9.4.4.5 COLUMBIA-SUICIDE SEVERITY RATING SCALE

All C-SSRS data will be listed. All scores and changes from baseline will be summarized by visit and arm, including the frequency of suicidal thoughts and suicide attempts.

9.4.4.6 VITAL SIGNS

The number of participants with substantial changes from baseline will be summarized and presented by arm and visit. Criteria for substantial change will be provided in the SAP. Substantial changes deemed clinically significant by the investigator will be recorded as AEs. Summary statistics for each vital sign and change from baseline for each visit will be presented by arm in tables and figures such as box plots and mean-plots over time.

9.4.4.7 AMERICAN UROLOGICAL ASSOCIATION SYMPTOMS INDEX

The total score and each individual question will be summarized descriptively by arm and scheduled visit.

9.4.4.8 OTHER SAFETY MEASURES

Any other significant physical or neurological examination findings will be presented by arm.

9.4.5 BASELINE DESCRIPTIVE STATISTICS

All baseline demographic, physical examination, medical history, epilepsy medication history, and clinical presentation variables will be presented in tabular form by study arm. Similar descriptives for participants in the OLE will be presented separately.

9.4.6 PLANNED INTERIM ANALYSES

The study database will be locked after the last patient completes the DBP visit in order to perform the primary analysis for the study. The treatment assignments will be unblinded for analysis purposes following the DBP database lock.

Safety data will be assessed periodically, through an SRC. This periodic review will include AEs, laboratory tests, vital signs, and ECG. If the blinded data suggests a potential safety or tolerability issue for XEN1101, an external group will perform an unblinded interim review of safety to provide further recommendations to the sponsor on a possible modification to the study that may include adjustment of randomization ratio, etc. The external independent reviewer may request additional trial data to better assess the benefit-risk of the patients in the study. The details on blinded and unblinded safety reviews, as well as the decision process, will be documented in the SRC charter and SAP.

9.4.7 SUBGROUP ANALYSES

The primary and secondary analyses will be repeated in the per protocol population to assess the impact of varying degrees of availability of seizure diary information and treatment adherence.

Effect of geographic region will be explored with efficacy and safety analyses.

Efficacy analyses may also be repeated separating those who have and have not had concomitant use of CYP3A4 inducer medication (ie, use of any of carbamazepine, eslicarbazepine, oxcarbazepine, phenytoin, topiramate, or phenobarbital).

9.4.8 TABULATION OF INDIVIDUAL PARTICIPANT DATA

All safety and efficacy data will be presented in patient-level listings.

9.4.9 EXPLORATORY ANALYSES

Details of exploratory analyses, including analyses of the OLE data, will be provided in the study SAP.

10 SUPPORTING DOCUMENTATION AND OPERATIONAL CONSIDERATIONS

10.1 REGULATORY, ETHICAL, AND STUDY OVERSIGHT CONSIDERATIONS

10.1.1 INFORMED CONSENT PROCESS

10.1.1.1 CONSENT/ASSENT AND OTHER INFORMATIONAL DOCUMENTS PROVIDED TO PARTICIPANTS

Consent forms describing in detail the study intervention, study procedures, and risks are given to the patient and written documentation of informed consent is required prior to starting intervention/administering study intervention. The following consent materials are submitted with this protocol:

- ICF.
- Pregnant partner ICF.

10.1.1.2 CONSENT PROCEDURES AND DOCUMENTATION

Informed consent is a process that is initiated prior to the individual's agreeing to participate in the study and continues throughout the individual's study participation. The ICF and any changes to the consent form made during the course of the study must be agreed to by Xenon and the Ethics Committee/Institutional Review Board (EC/IRB) prior to its use and must be in compliance with all International Council for Harmonisation Good Clinical Practice (ICH GCP), local regulatory requirements, and legal requirements.

The patient will be asked to read and review the ICF. The investigator must ensure that each patient is fully informed about the nature and objectives of the study and possible risks associated with participation and must ensure that the patient has been informed of his/her rights to privacy.

The investigator will explain the research study to the patient and answer any questions that may arise. A verbal explanation will be provided in terms suited to the patient's comprehension of the purposes, procedures, and potential risks of the study and of their rights as research patients. Patients will have the opportunity to carefully review the written consent form and ask questions prior to signing. The patients should have the opportunity to discuss the study with their family or surrogates or think about it prior to agreeing to participate. The patient will sign the informed consent document prior to any procedures being done specifically for the study. Patients must be informed that participation is voluntary and that they may withdraw from the study at any time, without prejudice. The original signed copy of the ICF must be maintained by the investigator and is participant to inspection by a representative of Xenon, their representatives, auditors, the EC/IRB, and/or health authorities. A copy of the ICF will be given to the patients for their records. The informed consent process will be conducted and documented in the source document (including the date), and the form signed, before the patient undergoes any study-specific procedures. The rights and welfare of the patients will be protected by emphasizing to them that the quality of their medical care will not be adversely affected if they decline to participate in this study.

10.1.2 STUDY DISCONTINUATION AND CLOSURE

This study may be temporarily suspended or prematurely terminated if there is sufficient reasonable cause. Written notification, documenting the reason for study suspension or termination, will be provided by the suspending or terminating party to the investigator, EC/IRB, and health authorities. If the study is prematurely terminated or suspended, the investigator will promptly inform study patients and the local EC/IRB and will provide the reason(s) for the termination or suspension. Study patients will be contacted, as applicable, and be informed of changes to the study visit schedule.

Circumstances that may warrant termination or suspension include, but are not limited to:

- Determination of unexpected, significant or unacceptable risk to patients.
- Demonstration of efficacy that would warrant stopping.
- Insufficient compliance to protocol requirements.
- Data that are not sufficiently complete and/or evaluable.
- Determination that the primary endpoint has been met.
- Determination of futility.

The study may resume once concerns about safety, protocol compliance, and data quality are addressed and satisfy the sponsor, EC/IRB, and/or health authorities.

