9.4.2 ANALYSIS OF THE PRIMARY EFFICACY ENDPOINT(S)

The monthly (28 days) seizure rate will be calculated separately in the baseline and DBP as the total number of focal seizures reported \times 28 / the total number of days seizure information is available in that period. The countable seizures for the primary endpoint will include focal aware seizures with motor signs, focal seizures with impaired awareness with or without motor signs, and focal seizures that lead to generalized tonic-clonic seizures.

Percent change from baseline will be calculated as (post-treatment monthly [28 days] focal seizure frequency – baseline monthly (28 days) focal seizure frequency) / baseline monthly (28 days) focal seizure frequency, so that a more negative number will represent greater benefit.

Primary analysis to test the null hypothesis as described in [Section 9.1](#) is based on the ITT population. Since the endpoint of percent change from baseline in monthly seizure count tends to be not normally distributed, an analysis of covariance (ANCOVA) model for the ranks of monthly (28 days) focal seizure frequency percent change from baseline will be used as the dependent variable, with baseline monthly (28 days) focal seizure frequency rank, arm (placebo, 10 mg, 20 mg, 25 mg), region, and background use of CYP3A4 inducer medication included as factors.

Under the assumption of a monotonic dose response relationship (true effect for the higher dose is not worse than the lower dose), the null hypothesis (H_{0123} : $MPC_{plac} = MPC_{10mg} = MPC_{20mg} = MPC_{25mg}$) will be tested based on linear contrast for the least square means (with coefficient of -3, -1, 1, 3 for placebo and the 3 treatment levels of 10, 20, and 25 mg) within the framework of the ranked ANCOVA model. Since only a positive dose response trend is of interest to demonstrate treatment effect, a 1-sided test with significance level of 0.05 will be used.

If a significant result is achieved ($p < 0.05$) under H_{0123} , the study will be considered positive and at least one dose level of XEN1101 should be better than placebo.

After H_{0123} is rejected, further testing (with the same significance level of 0.05) will be performed to formally test the pairwise difference H_{03} : $MPC_{plac} = MPC_{25mg}$, H_{02} : $MPC_{plac} = MPC_{20mg}$ and H_{01} : $MPC_{plac} = MPC_{10mg}$.

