MPC_{10mg} in sequential order ($H_{03} \rightarrow H_{02} \rightarrow H_{01}$) to assess whether each dose level is significantly better than placebo in percent reduction of monthly focal seizure count, within the same ANCOVA model. To control the type I error, only when the early null hypothesis is rejected, then the later hypothesis can be formally tested.

On the other hand, if the primary null hypothesis H_{0123} is not rejected, then additional formal statistical testing will not be performed. However, the nominal p-value comparing each of the doses versus placebo will still be provided for exploratory purposes.

With this a-priori specified stepwise testing procedure, the overall type I error will be controlled at 0.05 (1-sided).

Note that this study was designed as a Phase 2 study; therefore, 1-sided alpha of 0.05 was proposed to determine the efficacy of XEN1101. Further study will be needed to confirm the efficacy of XEN1101. It is the sponsor's understanding that in order for this study to be considered as a pivotal study, the 1-sided p-value will need to be <0.025 in favor of XEN1101.

Additional sensitivity analyses for the primary endpoint will be specified in the SAP.

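### Do the efficacy and futility termination grounds in Section 10.1.2 undo the one-sided 0.05 error control?

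*Combined protocol and SAP*

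**What the plan says.** Section 10.1.2 (Study Discontinuation and Closure) gives an open-ended list of circumstances that might justify suspending or terminating the study. Beside safety and data-quality grounds it has "Demonstration of efficacy that would warrant stopping", "Determination that the primary endpoint has been met" and futility. It names no look, threshold, data source or decision body, and does not say whether the DBP or the open-label extension (OLE) is meant.

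Section 9.4.6 (Planned Interim Analyses) describes the DBP database lock, followed by unblinding and the primary analysis, and periodic safety review. If blinded data point to a safety or tolerability problem, an external group reviews unblinded safety data and may recommend changes, including to the randomization ratio. In that setting, "The external independent reviewer may request additional trial data to better assess the benefit-risk of the patients in the study".

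Section 9.4.2 specifies a trend contrast in a ranked ANCOVA ("with coefficient of -3, -1, 1, 3 for placebo and the 3 treatment levels of 10, 20, and 25 mg"), for which "a 1-sided test with significance level of 0.05 will be used". The 25, 20 and 10 mg comparisons with placebo follow in that order, and "only when the early null hypothesis is rejected, then the later hypothesis can be formally tested". It concludes: "With this a-priori specified stepwise testing procedure, the overall type I error will be controlled at 0.05 (1-sided").

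**The concern.** Taken together, these sections seem to leave a route to an uncontrolled efficacy stop. The external reviewer can ask for data to weigh benefit against risk. Benefit here is seizure reduction, so the request could reach the primary endpoint by arm. Section 10.1.2 then lists demonstrated efficacy as a reason to terminate. No alpha is assigned to such a look, and Sections 9.4.6 and 10.1.6 do not say that efficacy results stay with the reviewer.

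If that route were used, the 0.05 statement would be wrong and the effect estimate from a trial stopped on a favourable result would be biased upward. Section 9.4.2 also mentions that a one-sided p-value below 0.025 would be needed for pivotal use, so a regulator might ask whether an efficacy look could have taken place.

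**Working it through.** **1. The plan's own figure.** Inputs from Section 9.4.2: one-sided level 0.05, fixed order of tests, one analysis.

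- Single look: P(Z > 1.645) = 0.0500.
- Stepwise tests: each later hypothesis is tested at 0.05 only after all earlier ones are rejected. A false rejection requires rejecting the first true null in the sequence, which has probability at most 0.05. The sequence adds nothing.
- Null simulation of the contrast: arms of 100/50/50/100 (placebo, 10, 20, 25 mg), ranks of percent change on arm and baseline rank, negative binomial counts with assumed dispersion θ = 5, 5,000 runs. Region and CYP3A4 inducer use were left out. The rejection rate was 0.0512. Its Monte Carlo standard error is √(0.05 × 0.95 / 5000) = 0.003, so this agrees with 0.05.

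The stated 0.05 is reproduced.

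**2. What an unplanned look would do.** With one look at information fraction t, the two statistics have correlation √t. If both are judged at 1.645, the overall error is 1 − P(Z₁ ≤ 1.645, Z₂ ≤ 1.645). The values of t and the number of looks are assumptions; the documents give none.

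| Assumed looks before the final test | Overall one-sided error |
|---|---|
| one, t = 0.50 (correlation 0.707) | 0.080 |
| one, t = 0.67 (correlation 0.819) | 0.074 |
| one, t = 0.75 (correlation 0.866) | 0.071 |
| two, equally spaced | 0.101 |
| three, equally spaced | 0.117 |

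At one-sided 0.025, one look at t = 0.50 gives 0.042.

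**3. Futility.** Stopping when Z₁ < 0 at t = 0.50 gives an error of P(Z₁ > 0, Z₂ > 1.645) = 0.049. A futility stop costs power and does not inflate type I error, so this ground does not support the concern.

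**4. Does the plan contain such a look?** The relevant sections say:

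- Section 9.1: the primary endpoint is analysed once all enrolled participants have finished the DBP or been withdrawn.
- Section 9.4.6: treatment codes are opened for analysis after the DBP lock.
- Section 6.3: patients, investigators, sponsor and CRO staff stay blinded during the DBP, apart from one pre-identified individual at the sponsor. Blinding to prior assignment continues in the OLE until the DBP lock.
- Section 7.1, the one headed as a stopping rule: the quarterly committee works on blinded data, and an arm would be stopped only for a major safety issue confirmed by independent unblinded assessment.
- Section 10.1.6: the person unblinded for safety is an external clinician, independent of the company and the study team, who makes recommendations.

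None of these produces an efficacy test before the lock, and none connects the safety review to the efficacy grounds in Section 10.1.2.

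**5. Can those grounds apply after the lock?** Yes. The OLE runs from Day 56 to a last scheduled dose on Day 1148, that is 1148 − 56 = 1092 days, or 156 weeks, per patient. Section 9 has the DBP analysed when that part is complete. A finding that the primary endpoint was met can therefore arise while the OLE is still running, and closing the study then has no effect on alpha.

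**The case for a change.** The strongest opposing case is that a protocol should not list grounds it has no valid way to act on. Section 10.1.2 does not confine the efficacy grounds to the period after the lock. The external reviewer's data request has no stated limit, and nothing in the protocol bars efficacy from influencing a recommendation to the sponsor. Two or three sentences would settle this, and the possible pivotal use makes the ambiguity less comfortable.

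The textual part stands: the wording is loose and the sections could be better aligned. Three things keep it from being a defect in the analysis. A data request spends no alpha; only an efficacy-based stop or change would matter, and the plan provides for none. Section 9.4.6 sends the detail of the reviews to the Safety Review Committee charter and the SAP. The charter and the separate SAP announced in Section 9 are not in the text reviewed, so one cannot say that a firewall is missing, only that the protocol does not state one. And Section 9.4.2 says a further study will be needed to confirm efficacy, so pivotal use is a conditional remark.

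Adding randomization stage to the rank ANCOVA if the allocation ratio changes is a separate, contingent question for the SAP. No harm from leaving it out has been shown here.

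**Conclusion.** The concern does not call for a change. Carried out as written, the plan has one efficacy analysis, and its one-sided error is 0.05 as claimed. The figures of 0.071 to 0.080 for one look, and up to 0.117 for three, describe a trial in which someone takes an unplanned efficacy look and stops at an unadjusted 0.05. That would be a departure from Sections 9.1 and 9.4.6. The futility ground carries no type I error cost in any case.

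This conclusion assumes that no efficacy-based stop or design change is made before the DBP lock, and that any data given to the external reviewer serve the safety question that triggered the review. Saying so in Section 10.1.2 or in the committee charter would be reasonable tidying if the protocol is amended for other reasons, but it would alter no test, estimate or sample size.

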10.1.3 CONFIDENTIALITY AND PRIVACY

Data collected during this study may be used to support the development, registration, or marketing of the medicinal product. Xenon will control all data collected during the study, and will abide by the Applicable Data Protection Laws, including the General Data Protection Regulation (GDPR) in the European Union, the Health Insurance Portability and Accountability Act in the US and the Personal Information Protection and Electronic Documents Act (PIPEDA) in Canada. For the purpose of the Applicable Data Protection Law, Xenon will be the data controller. To the extent that the CRO processes personal data on behalf of Xenon, in relation to such data the CRO shall only act in accordance with the terms of this protocol and Xenon's reasonable written instructions; the CRO shall take appropriate technical and organizational measures against the unauthorized or unlawful processing of such personal data.

De-identification will be assured by assignment of a unique number to each patient at screening, which will be used for all patient related data collected in the study database. After obtaining patient informed consent, the investigator or the investigator's designee will access the electronic data capture (EDC) system at screening to obtain the patient's unique ID number, consisting of a 5-digit site identifier and 4-digit sequentially assigned subject number. Following confirmation of study entry criteria, the Investigator or the investigator's designee will utilize the EDC system to randomize the patient into the study. During this contact, the investigator or designee will provide the unique patient ID number assigned at screening. Patients will be assigned to receive their treatment according to the randomization schedule.

After patients have consented to take part in the study, their medical records and the data collected during the study will be reviewed by Xenon and/or its representatives. These records and data may, in addition, be reviewed by the following: independent auditors who validate the data on behalf of Xenon, health authorities, and the EC/IRB. The sponsor will only receive de-identified patient information; the code list that links the patient's personal information to the study will be securely stored and kept confidential with the investigator and the investigator's designee.

Although patients will be known by a unique number, their year of birth may also be collected and used to verify the accuracy of the data; for example, that the results of study assessments are assigned to the correct patient. The results of this study, containing the unique number, year of birth and relevant medical information including ethnicity, may be recorded and transferred to and used in other countries throughout the world, which may not afford the same level of protection. The purpose of any such transfer would be to support regulatory submissions made by Xenon in such countries.

10.1.4 FUTURE USE OF STORED SPECIMENS AND DATA

With the patient's consent and as approved by the EC/IRB, de-identified PK plasma samples will be stored at Xenon's designated bioanalytical laboratory. These samples could be used for tests other than planned PK analysis, such as profiling of drug binding proteins, bioanalytical method validation purposes, stability assessments, metabolite assessments, and/or to assess other actions of XEN1101 with plasma constituents. The unique patient ID number will be used to ensure linking the biological specimens with the phenotypic data from each patient, maintaining the blind of the identity of the patient.

Blood samples from patients who provide additional consent for genotype and biomarker assessments will be stored and analyzed at Xenon's designated bioanalytical laboratory as described in [Section 8.3.8](#) above.

10.1.5 KEY ROLES AND STUDY GOVERNANCE

A Steering Committee will be formed to provide oversight of the conduct of the clinical trial. This may include oversight of the practical aspects of the study as well as ensuring that the study is conducted in a way that is both safe for the patients and provides appropriate safety and efficacy data to the sponsor and investigators (refer to the Steering Committee Charter).

10.1.6 SAFETY OVERSIGHT

Investigators are responsible for monitoring the safety of patients who have entered the study and for alerting the sponsor (or designee) to any event that seems unusual, even if this event may be considered an unanticipated benefit to the patient. The investigator is responsible for the appropriate medical care of patients during the study. The sponsor or medically qualified designee will monitor safety data throughout the course of the study. Safety data will be reviewed periodically and include at a minimum, SAEs, trends in AEs, and laboratory results (refer to the Medical Monitoring Plan). Reports will be provided to the Steering Committee per an agreed upon schedule, but no less than twice per year.

Additionally, the sponsor will implement a SRC, to meet on a quarterly basis to review ongoing safety data/trends from the study. The SRC may choose to convene an unscheduled meeting as required, to review and discuss any urgent potential safety issues that have arisen during the course of the study. In addition to the sponsor representatives, the SRC will also consist of an independent physician, as described in the SRC charter.

In the event that blinded data suggests a potential tolerability issue for XEN1101, safety data will be unblinded to a designated external clinician who is independent from the company and the study team to provide further recommendation to sponsor on potential modification to the study. This may include adjustment to the current randomization ratio. The details on blinded and unblinded safety review, as well as the decision process will be documented in the SRC charter.

